### Changes in vital signs, ECG, physical examination, and laboratory test results

Changes in vital signs, ECG, physical examination and laboratory tests will be recorded as an AE in the eCRF, if they are judged clinically relevant by the investigator.

### Adverse Events of Special Interest (AESIs)

Although rare, drug-induced liver injury is under constant surveillance by sponsors and regulators and is considered as AESI. Timely detection, evaluation, and follow-up of laboratory alterations of selected liver laboratory parameters to distinguish an effect of the underlying malignancy on liver function from other causes are important for patient safety.

The following are considered as AESIs:

Hepatic injury defined by the following alterations of liver parameters: Hepatic injury defined by the following alterations of liver parameters:

- For patients with normal liver function (ALT, AST and bilirubin within normal limits) at baseline an elevation of AST and/or ALT >3 fold ULN combined with an elevation of bilirubin >2 fold ULN measured in the same blood draw sample. Patients showing these lab abnormalities need to be followed up according to [Appendix 10.9](#) of this clinical trial protocol and the "DILI checklist" provided in the ISF.
- For patients with abnormal liver function at baseline an elevation of AST and/or ALT >5 fold ULN combined with an elevation of bilirubin >2 fold ULN measured in the same blood draw sample. Patients showing these lab abnormalities need to be followed up according to [Appendix 10.9](#) of this clinical trial protocol and the "DILI checklist" provided in the ISF.

AESIs are to be reported in an expedited manner similar to Serious Adverse Events, even if they do not meet any of the seriousness criteria - for details please see Chapter 5.2.2.2.

If the investigator determines any AESI is related to study drug, the administration of the study drug must be managed according to [Section 4.1.4](#) of the protocol.

#### 5.2.2.2 Adverse event and serious adverse event reporting

All adverse events, serious and non-serious, occurring during the course of the clinical trial (i.e., from signing the informed consent through to the Follow-up) will be collected, documented and reported to the sponsor by the investigator on the appropriate CRF(s) / eCRFs / SAE reporting forms. Serious AEs and AESIs occurring later than 28 days after the last administration of study drug will only be reported if deemed to be related to study drug. Following approval of Protocol Version 3.0 and after the individual patient's end of trial, the investigator does not require to actively monitor the patient for AEs but should only report relevant SAEs and AESIs that the investigator may become aware of. Reporting will be done according to the specific definitions and instructions detailed in the 'Adverse Event

**Proprietary confidential information.**

© 2016 **Boehringer Ingelheim International GmbH** or one or more of its affiliated companies. All rights reserved.

This document may not - in full or in part - be passed on, reproduced, published or otherwise used without prior written permission.

Reporting' Section of the Investigator Site File. A diagram of the reporting requirements is provided in [Appendix 10.7](#).

For each adverse event, the investigator will provide the onset date, end date, intensity, treatment required, outcome, seriousness, and action taken with the investigational drug. The investigator will determine the relationship of the investigational drug to all AEs as defined in [Section 5.2.2.1](#).

The investigator also has the responsibility to report AEs according to the table below and [Appendix 10.7](#):

Table 5.2.2.2: 1 AE/SAE Reporting

Time period	Reporting requirements
From signing of informed consent through to 28 days after last trial drug administration	Report all AEs, SAEs and AESIs regardless of relatedness or whether the trial drug was administered. This includes all deaths.
Post-treatment (>28 days after last trial drug administration)	Report only SAEs and AESIs which are considered related to trial treatment that the investigator may become aware of.  Death should be reported as an SAE only when considered related to trial treatment (because death is an endpoint and will be followed-up separately).

Any AEs reported to the sponsor during this phase must be documented in the safety database.

The investigator must report the events via telephone/fax using the SAE form immediately (within 24 hours) to the sponsor: SAEs, AESIs and non-serious AEs occurring at the same time as an SAE or AESI and/or which are medically related to the SAE or AESI. With receipt of any further information to these events, a follow-up SAE report has to be provided. SAEs, AESIs and non-serious AEs must include a causal relationship assessment made by the investigator.

BI has set up a list of AEs which are defined to be always serious. In order to support the investigator with the identification of these "always serious adverse events", if a non serious AE is identified to be serious per BI definition, a query will be raised. The investigator must verify the description and seriousness of the event. If the event description is correct, the item "serious" needs to be ticked and an SAE has to be reported in expedited fashion following the same procedure as above.

The list of these adverse events can be found via the RDC-system.

**Proprietary confidential information.**

© 2016 Boehringer Ingelheim International GmbH or one or more of its affiliated companies. All rights reserved.

This document may not - in full or in part - be passed on, reproduced, published or otherwise used without prior written permission.

The SAE form is to be forwarded to the defined unique entry point identified for the BI OPU (country-specific contact details will be provided in the Investigator Site File). This immediate report is required irrespective of whether the investigational product has been administered or not and irrespective of causal relationship. It also applies if new information to existing SAEs becomes available.

### Pregnancy

In rare cases, pregnancy might occur in clinical trials. Once a female subject has been enrolled into the clinical trial, after having taken study medication, the investigator must report immediately any drug exposure during pregnancy to the sponsor. Drug exposure during pregnancy has to be reported immediately (within 24 hours or next business day whichever is shorter) to the defined unique entry point for SAE forms of the respective BI OPU (country-specific contact details will be provided in the Investigator Site File). The outcome of the pregnancy associated with the drug exposure during pregnancy must be followed up. In the absence of an (S)AE, only the Pregnancy Monitoring Form for Clinical Trials and not the SAE form is to be completed. The ISF will contain the Pregnancy Monitoring Form for Clinical Trials (Part A and Part B).

### **5.2.3 Assessment of safety laboratory parameters**

Safety laboratory samples will be analyzed at a central laboratory (Quest Diagnostics). Safety laboratory examinations will include haematology, biochemistry and urine examinations. [Table 5.2.3: 1](#) presents the laboratory tests to be performed.

After approval of Protocol Version 3.0, the safety laboratory samples will be analyzed in a laboratory facility at or nearby the investigational site; provided that the laboratory is appropriately certified and reference ranges are available.

**Proprietary confidential information.**

© 2016 Boehringer Ingelheim International GmbH or one or more of its affiliated companies. All rights reserved.

This document may not - in full or in part - be passed on, reproduced, published or otherwise used without prior written permission.

Table 5.2.3: 1 Clinical laboratory tests

Category	Parameters
Hematology	haemoglobin, haematocrit, platelet count, white blood cell count (WBC). At screening only: neutrophils
Coagulation	International Normalized Ratio (INR), activated Partial Thromboplastin Time (aPTT)
Chemistry	
Electrolytes	sodium, potassium, calcium, magnesium
Liver function tests	alkaline phosphatase, aspartate aminotransferase (AST), alanine aminotransferase (ALT), $\gamma$ -glutamyltransferase (GGT), total bilirubin
Renal function parameters	blood urea/blood urea nitrogen (BUN), creatinine; Glomerular Filtration Rate (GFR) will be estimated utilising serum creatinine values (see Appendix 10.3 )
Other	glucose, albumin
Urinalysis	pH, protein, glucose, blood, leucocytes, nitrite, in case of pathological finding further evaluation should be performed and results documented
Pregnancy test	$\beta$ -HCG testing in urine or serum in women of childbearing potential ( WOCBP)

The investigator should complete additional evaluations of laboratory tests as clinically indicated. Any abnormal findings from these investigations need to be reported as an Adverse Event.

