## CLINICAL TRIAL PROTOCOL SYNOPSIS

Name of company: Boehringer Ingelheim		Tabulated Trial Protocol	
Name of finished product: Giotrif® / Gilotrif®, Afatinib			
Name of active ingredient: BIBW 2992			
Protocol date: 15 Nov 2011	Trial number: 1200.125		Revision date: 24 June 2016
Title of trial:	LUX-Lung 8: A randomized, open-label Phase III trial of afatinib versus erlotinib in patients with advanced squamous cell carcinoma of the lung as second-line therapy following first-line platinum-based chemotherapy		
Co-ordinating Investigators:			
Trial sites:	Multi-center trial		
Clinical phase:	III		
Objectives:	
Primary: Compare efficacy of afatinib with erlotinib as second-line treatment for patients with squamous cell carcinoma of the lung, as measured by progression-free survival (PFS).
 
Key secondary: Compare overall survival (OS) in both treatment groups
 
Secondary: Objective response rate (ORR), disease control rate (DCR), tumour shrinkage and the assessment of Health-related Quality of Life (HRQoL) and safety in both treatment groups
		
Methodology:	Randomised, open-label, active control study comparing afatinib vs. erlotinib. Eligible patients will be randomized to receive either afatinib or erlotinib in a 1:1 ratio. Independent assessment of the primary endpoint will be completed in a treatment-blinded manner. Randomization will be stratified based on race (Eastern Asian vs. non-Eastern Asian).		
No. of patients:			
total entered:	795		
each treatment:	Afatinib: 398 Erlotinib: 397		
Diagnosis :	Patients with diagnosis of advanced NSCLC squamous or mixed histology, who have completed at least 4 cycles of platinum-based doublet chemotherapy and who are eligible to receive 2 nd line therapy.		

Proprietary confidential information.

© 2016 Boehringer Ingelheim International GmbH or one or more of its affiliated companies. All rights reserved.

This document may not - in full or in part - be passed on, reproduced, published or otherwise used without prior written permission.

Name of company: Boehringer Ingelheim		Tabulated Trial Protocol	
Name of finished product: Giotrif ® / Gilotrif ® , Afatinib			
Name of active ingredient: BIBW 2992			

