#### 4.2.3 Management of expected adverse events

Dermatologic adverse events and diarrhoea are the most common side-effects associated with treatment with afatinib. Treatment of these side-effects should be proactive and should be started as early as possible after onset of symptoms.

The most common adverse events in NSCLC patients receiving erlotinib are rash and diarrhoea, anorexia, fatigue, dyspnea, cough, nausea, infection and vomiting ([R11-1186](#)). Refer to the Tarceva package insert for management of these events.

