**Proprietary confidential information.**

**© 2016 Boehringer Ingelheim International GmbH or one or more of its affiliated companies. All rights reserved.**

This document may not - in full or in part - be passed on, reproduced, published or otherwise used without prior written permission.

Table 4.2.3.1: 1 Grade specific treatment of study-drug related diarrhoea

Severity (CTCAE Grading)	Description	Intervention concerning afatinib treatment	Specific intervention
Mild (Grade 1)	Increase of < 4 stools per day over baseline; mild increase in ostomy output compared with baseline	Continue same dose	Stop laxatives and advise patient to drink at least 8-10 glasses of clear fluids per day; 4 mg (2 Tablets) of loperamide to be taken immediately, followed by 2 mg (1 Tablet) after each loose stool until bowel movements cease for 12 hours
Moderate (Grade 2)	Increase of 4-6 stools per day over baseline; iv. fluids indicated < 24 hours; moderate increase in ostomy output compared with baseline; not interfering with ADL	Continue same dose unless Grade 2 diarrhoea continues for <math>\geq 2</math> days (48 hours) in which case treatment must be interrupted until recovered to $\leq$ Grade 1 followed by dose reduction	Continue loperamide; assess for dehydration and electrolyte imbalance; consider iv fluids and electrolyte replacement
Severe (Grade 3)	Increase of $\geq 7$ stools per day over baseline; incontinence; iv fluids > 24 hours; hospitalization; severe increase in ostomy output compared with baseline; interfering with ADL	Dose interruption until recovered to $\leq$ Grade 1 followed by dose reduction 	See Grade 2; plus: an infectious process should be ruled out with stool cultures; aggressive iv fluid replacement $\geq 24$ hours; hospitalization to monitor progress; consider prophylactic antibiotics if patient is also neutropenic;
Life threatening (Grade 4)	Life-threatening consequences (e.g. haemodynamic collapse)	Dose interruption until recovered to $\leq$ Grade 1 followed by dose reduction 	See Grade 3

If despite optimal supportive care and a treatment interruption, diarrhoea does not resolve to CTC AE Grade  $\leq 1$  within 14 days, treatment with afatinib must be permanently discontinued.

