## 5.2 SAFETY

### 5.2.1 Endpoints of safety

Safety of afatinib and erlotinib will be evaluated by intensity and incidence of adverse events, graded according to NCI CTCAE version 3.0 ([R04-0474](#)). Safety endpoints include:

- The overall incidence and intensity of adverse events
- Gastrointestinal events (vomiting, nausea, diarrhoea)
- Skin reactions (rash, acne)

Tolerability of afatinib and erlotinib will be assessed based on dosage reduction and discontinuation due to adverse events.

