#### 5.2.4 Electrocardiogram

12-lead ECGs will be taken at the time points specified in the [flow chart](#) if clinically indicated. ECGs will be completed locally at the study sites. The investigator will review the ECG recording at the time of the visit and record any ECG abnormality that meets AE criteria.

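### Protocol Sections 5.2.2.1 and 5.2.3 conflict on when an abnormal laboratory result is an adverse event, so laboratory-type AE incidence depends partly on how often sites draw extra tests

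*Protocol*

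**What the plan says.** Three places in the protocol say when a test result becomes an AE.

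- Section 5.2.2.1, in the paragraph on changes in vital signs, ECG, physical examination and laboratory results, says that such changes "will be recorded as an AE in the eCRF, if they are judged clinically relevant by the investigator".
- Section 5.2.3, in the text after Table 5.2.3: 1, says "The investigator should complete additional evaluations of laboratory tests as clinically indicated" and then adds "Any abnormal findings from these investigations need to be reported as an Adverse Event".
- Section 5.2.4 asks the investigator to review each ECG and "record any ECG abnormality that meets AE criteria", which keeps a filter for that assessment.

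The affected quantity is a named safety endpoint. The first entry in Section 5.2.1 is "The overall incidence and intensity of adverse events". SAP Section 7.8.1 tabulates it by treatment, system organ class, preferred term and highest CTC grade. The synopsis describes the trial as "Randomised, open-label, active control study comparing afatinib vs. erlotinib", so the person deciding whether to order an extra test knows the treatment.

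**The concern.** An AE definition should depend on what happened to the patient and not on why the blood was drawn. Here a potassium just below the reference range, thought unimportant by the investigator, is not an AE at a scheduled visit but must be reported as one if it came from an additional test. Sites that test more will then record more AEs from the same patients. Because testing is discretionary and treatment is known, differences in testing habits between sites, or between arms within a site, can enter the AE tables as if they were differences in toxicity. The terms most exposed are low-grade electrolyte, renal, liver and haematology terms.

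AE status also feeds reporting. Section 5.2.2.2 requires non-serious AEs that coincide with a serious AE to be sent on the SAE form within 24 hours. Read literally, minor out-of-range values from extra tests during a serious event would fall under that rule.

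**Working it through.** The documents state no figure on this point, so there is none to reproduce. The check is a comparison of the texts, followed by an illustration of what the literal wording implies.

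**Step 1: the rules side by side.**

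| Source of the result | Protocol section | Filter before it is an AE |
|---|---|---|
| Laboratory change in general | 5.2.2.1 | Investigator judges it clinically relevant |
| Additional laboratory test | 5.2.3 | None; any abnormal finding |
| ECG | 5.2.4 | Must meet AE criteria |

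The rule for additional tests is mandatory and unfiltered, and nothing elsewhere gives one rule precedence. If the investigations meant in 5.2.3 were taken to be all laboratory tests, the conflict with 5.2.2.1 would be wider.

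**Step 2: dependence on testing frequency.** Let q be the chance that one extra draw shows any abnormal finding, and m the number of extra draws. With independent draws, P(at least one such AE) = 1 − (1 − q)^m. The documents give neither q nor m; the values below are assumptions.

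| q | m = 1 | m = 2 | m = 4 |
|---|---|---|---|
| 5% | 5.0% | 9.8% | 18.5% |
| 20% | 20.0% | 36.0% | 59.0% |
| 50% | 50.0% | 75.0% | 93.8% |

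For example, at q = 20% and m = 4: 1 − 0.8^4 = 59.0%. The dependence on m follows directly from the wording.

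**Step 3: difference between arms.** Let the number of extra draws per patient be Poisson with mean λ. The share of patients with at least one such AE is then 1 − exp(−λq). Afatinib minus erlotinib, in percentage points:

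| Mean extra draws, afatinib vs erlotinib (assumed) | q = 5% | q = 20% | q = 50% |
|---|---|---|---|
| 1 vs 1 | 0.0 | 0.0 | 0.0 |
| 1.5 vs 1 | +2.3 | +7.8 | +13.4 |
| 1 vs 1.5 | −2.3 | −7.8 | −13.4 |
| 2 vs 1 | +4.6 | +14.8 | +23.9 |
| 1 vs 2 | −4.6 | −14.8 | −23.9 |

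For example, 1.5 vs 1 at q = 20%: exp(−0.20) − exp(−0.30) = 0.819 − 0.741 = 0.078. With q equal in both arms, the sign is set entirely by the testing rates, which the documents do not give.

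**Step 4: do the documents indicate which arm is tested more?** They contain prompts for both drugs.

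- Afatinib: a renal-function trigger in Table 4.1.4.1.2: 1, and the instruction in Table 4.2.3.1: 1 to "assess for dehydration and electrolyte imbalance" from Grade 2 diarrhoea. The text around that table concerns afatinib.
- Erlotinib: regular PT and INR checks for patients on coumarin-type anticoagulants (Section 4.2.2.1), and separate bilirubin, transaminase and dehydration triggers in Table 4.1.4.2.1: 1.
- Both: the same trigger of Grade 2 diarrhoea lasting 48 hours in the two dose tables.

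These prompts cannot be turned into a testing rate for either arm.

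**The case against.** The strongest reply is that 5.2.3 concerns tests done because something was clinically suspected, so a lower reporting threshold may be deliberate. Planned safety samples went to a central laboratory until Protocol Version 3.0, and the documents do not say how additional results reach the database. The AE form may be their route of capture. This has some force and shapes the fix. It does not remove the conflict: a good reason to draw a panel does not make every out-of-range analyte on it relevant, and the protocol does not say that the difference is intended.

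The second reply is that little depends on it, and this largely stands. SAP Section 7.8.1 makes AE analyses descriptive and counts patients rather than events, so repeat findings under the same term add nothing. Grades 3, 4 and 5 are shown separately, away from the low grades most affected. Overall AE incidence may have little room to move: in the afatinib trial cited in Section 4.1.3, a different population, diarrhoea alone affected 93.9% to 96.7% of patients. SAP Section 7.8.2 analyses laboratory values with its own threshold (CTCAE grade 2 or higher with at least a one-grade rise) and does not use the AE rule. That analysis does not, however, correct the preferred-term AE tables.

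A reader might go further and infer that AE incidence is inflated in the afatinib arm, since the diarrhoea table prompts electrolyte checks while for erlotinib Section 4.2.3 says "Refer to the Tarceva package insert for management of these events". The documents do not support this. The 5.2.3 rule is the same for both arms and erlotinib has its own prompts. The table's title refers to study-drug related diarrhoea, and only its dose column names afatinib. Whether the package insert prompts less testing cannot be judged from these documents. The rationale in Section 2.1 also describes the AE profiles as comparable.

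**Conclusion.** The conflict is real and unresolved: under 5.2.3 an additional test turns any abnormal value into an AE, while 5.2.2.1 requires clinical relevance. As written, the incidence of laboratory-type AEs is partly a measure of testing intensity. In an open-label trial with discretionary testing, that intensity may differ by site or arm.

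The direction and size of any between-arm effect are unknown. The percentages in the working show a mechanism under assumed values of q, m and λ, with independent draws and the same q in both arms. They are not estimates for this trial and reverse sign when the assumed testing rates are swapped.

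This is a minor point. It affects the descriptive preferred-term tables for laboratory-type AEs, chiefly at low grade. It does not affect PFS, OS or the graded laboratory analysis.

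**What to change.** Use one AE criterion for laboratory results from scheduled and additional tests. The simplest way is to replace the last sentence of Section 5.2.3 with, for example: Abnormal findings from these investigations are reported as AEs if the investigator judges them clinically relevant, as in Section 5.2.2.1. The hepatic injury AESI criteria in Section 5.2.2.1 stay unchanged.

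If the lower threshold for additional tests is intended, the protocol should say so and explain how the AE tables are to be read in that light.

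The cost is one sentence. The downside is that minor out-of-range values from unscheduled tests would no longer appear as AEs, although clinically relevant ones still would. The sponsor should therefore confirm that additional-test results are captured as laboratory data, so that removing the AE requirement does not lose them.

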#### 5.2.4 Electrocardiogram

12-lead ECGs will be taken at the time points specified in the [flow chart](#) if clinically indicated. ECGs will be completed locally at the study sites. The investigator will review the ECG recording at the time of the visit and record any ECG abnormality that meets AE criteria.

#### 5.2.5 Assessment of other safety parameters

##### 5.2.5.1 Physical Examination, Performance Status

A full physical exam must include cardiopulmonary examination, examination of the regional lymph nodes, examination of the abdomen, and an assessment of the mental and neurological

Proprietary confidential information.

© 2016 Boehringer Ingelheim International GmbH or one or more of its affiliated companies. All rights reserved.

This document may not - in full or in part - be passed on, reproduced, published or otherwise used without prior written permission.

status. Additional symptoms which have not been reported during a previous examination must be clarified. Wherever possible the same investigator should perform this examination.

A complete physical examination will be done as indicated on the [flow chart](#). A symptom-directed examination is to be performed at all other visits as indicated in the flow chart.

